9.3 VITAL SIGNS

All subjects in the Safety population will be included in the vital signs analysis.

9.3.1 Measurements

Vital signs will consist of blood pressure (systolic and diastolic blood pressure, mmHg), heart rate (beats per minute (bpm)), respiratory rate (breaths/min), temperature (°C) and weight. At

screening, vital signs will be assessed in the supine position after the subject has rested for at least 3 minutes. Blood pressure and pulse will be assessed again after three minutes in the standing position. At other time points, vitals will be measured after 3 minutes supine rest. Vitals should be completed within +/- 30 minute of schedule timing to avoid overlapping.

Height and weight (without shoes) will be collected at Screening and BMI will be calculated. Height, weight and BMI will be collected and calculated at other time points (check-in, follow-up and ET visit).

9.3.2 Collection Schedule

For SAD, vital signs on screening, Day -1 (at the time of admission), Day 1 (pre-dose, 30 min, 1, 2, 4, 6, 8, 12 and 24 hrs post dose), Day2, Day 3, Day 5, Day 8 and Day 15. For MAD, vital signs on screening, Day -1 (at the time of admission), Day 1 & Day 2 (pre-dose, 30 min, 1, 2, 4, 6, 8, 12 and 24 hrs post dose), Day 3, Day 4, Day 5, Day 6, Day 7 (pre-dose, 30 min, 1, 2, 4, 6, 12 hrs post dose), Day 8, Day 9, Day 11 and Day 15. Assessment times for vital sign parameters are presented below in Table 4 & 5.

Table 4. Vital Sign Assessment Times (SAD)

Visit/Day	Vital Sign Assessment Times
Screening	✓
Check-in Day -1	✓
Day 1 (Treatment)	pre-dose, 30 min, 1, 2, 4, 6, 8, 12 and 24 hrs post dose
Day 3 (Discharge)	✓
Day 5	✓
Day 8	✓
Day 15	✓

Table 5. Vital Sign Assessment Times (MAD)

Visit/Day	Vital Sign Assessment Times
Screening	✓
Check-in Day -1	✓

 
Statistical Analysis Plan
	
Sponsor: Rhizen Pharmaceuticals SA
 
Study: Study 15-MR-001

--	---

Day 1 (Treatment)	Pre-dose, 30 min, 1, 2, 4, 6, 8, 12 and 24 hrs post dose
Day 3 (Treatment)	✓
Day 4 (Treatment)	✓
Day 5 (Treatment)	✓
Day 6 (Treatment)	✓
Day 7 (Treatment)	Pre-dose, 30 min, 1, 2, 4, 6, 8, 12 and 24 hrs post dose
Day 8 (Discharge)	✓
Day 9	✓
Day 11	✓
Day 15	✓

9.3.3 Derived and Imputed Data

Baseline will be defined as the last non-missing observation prior to the dosing on Day 1.

9.3.4 Data Summarization and Presentation

Vital signs data will be listed chronologically by cohort/treatment, subject, visit/day, and time point when applicable.

Baseline values, absolute values and change from baseline for each post-dose time point will be summarized by treatment group using standard descriptive statistics. Off-treatment vital signs (e.g., Screening, Day -1, Unscheduled visit) will be listed but not otherwise analyzed. No inferential tests will be conducted.

Weight (without shoes) is measured at screening, check-in, follow-up and ET visit, the screening observation is used to summarize demographics, and the last non-missing observation prior to dosing on Day 1 (mostly likely the check-in observation) is defined as baseline to calculate weight change at post-dosing visits.

9.4 ECG

All subjects in the Safety population will be included in the ECG analysis.

For SAD, a standard 12-lead ECG will be performed with the subject in a supine position at

Screening, Day -1 (at the time of admission), Day 1 (pre-dose, 15, 30, 45 min, 1, 2, 4, 6, 8, 12 and 24 hrs post dose), Day 3, Day 5, Day 8 and Day 15 or Early Termination. For MAD, a standard 12-lead ECG will be performed with the subject in a supine position at Screening, Day -1 (at the time of admission), Day 1 (pre-dose, 15, 30, 45 min, 1, 2, 4, 6, 8, 12 and 24 hrs post dose), Day 5, Day 7 (pre-dose, 15, 30, 45 min, 1, 2, 4, 6, 8, 12 and 24 hrs post dose), Day 8 and Day 15 or Early Termination. Triplicate ECG will be taken 1 minute apart on screening, Day 1 (pre-dose) and for confirmation of abnormality detected in the single ECG measurement based on Investigator judgement.

For each assessment, the ECG will be reviewed by the qualified physician and the interpretation will be recorded in the eCRF as normal, abnormal but not clinically significant, abnormal and clinically significant. In addition, the standard ECG parameters including ventricular rate (VR), and intervals for PR, QRS, QT, and QTcB (Bazette's corrections for heart rate) will be recorded.

Baseline will be defined as the last non-missing observation prior to dosing on Day 1.

All ECG data will be listed chronologically by cohort/treatment, subject, visit/day, and time point. Abnormal ECG results will be provided in a separate listing.

Overall interpretation of ECG measurements will be summarized by treatment at each time point using frequencies. Baseline values, absolute values, and CFB will be summarized by treatment group using standard descriptive statistics for VR, PR interval, QRS duration, and QT interval. Off-treatment ECG data (e.g., Screening, Day -1, and Unscheduled visits) will be listed but not otherwise analyzed. No inferential tests will be conducted on ECG data.

9.5 PHYSICAL EXAMINATION

For SAD, a complete physical examination will be performed at screening, Day -1, Day 3, Day 8 and Day 15, or if necessary at the Early Termination visit. For MAD, a complete physical examination will be performed at screening, Day -1, Day 4, Day 8 and Day 15, or if necessary at the Early Termination visit. This exam will include general appearance, skin, neck (including thyroid), eyes, ears, nose, throat, lungs, heart, abdomen, back, lymph nodes, extremities, vascular, and neurological. If indicated based on medical history and/or symptoms, rectal, external genitalia, breast, and/or pelvic exams may be performed. Information for all physical examinations must be included in the source documentation at the study site and will not be recorded the CRF. Significant findings that are present prior to informed consent are included in the Relevant Medical History CRF. Significant findings observed after informed consent signature which meet the definition of an Adverse Event must be appropriately recorded on the Adverse Event CRF. No listings and summary tables will be produced separately.

9.6 COGNITIVE TEST

A cognitive test (e.g. Mini-Mental State Examination (MMSE)) will be performed at Screening and Day 3 (SAD)/ Day 8 (MAD) to assess the effect of drug on cognitive function.

MMSE data will be listed chronologically by cohort/treatment, subject, and visit/day. The classification of MMSE results as normal/abnormal follows the rules in Table 6. Such information will also be included in the listing.

Baseline will be defined as the observation collected at screening. Baseline values, absolute values, and CFB will be summarized by treatment group using standard descriptive statistics. No inferential tests will be conducted on MMSE data.

Table 6. Classification of Normal/Abnormal MMSE Results

Classification	Description	Rules
Normal	No cognitive impairment	Score 24-30 (inclusive)
Abnormal	Cognitive impairment	Score <24

10 EXPLORATORY ANALYSES

Exploratory assessments will be conducted on blood biomarkers (Th1, Th2 and Th 17 cytokines) in MAD part only. Blood samples will be collected at baseline (Day1, pre-dose), and Day 7 (pre-dose and 4 hrs post dose). See laboratory manual for biomarker processing instructions.

In the descriptive analysis, two types of baselines are considered to calculate CFB values. First, set Day 1 pre-dose value as baseline and calculate CFB for all collection time points after the first dosing on Day 1. Second, set Day 7 pre-dose value as baseline and calculate CFB for the 4-hour post-dose time point on Day 7. Descriptive statistics (number of observations, mean, standard deviation, median, minimum and maximum) will be provided for baseline (Day 1, pre-dose), Day 7 (Pre-dose), change from Baseline to Day 7 (Pre-dose), Day 7 (4 hrs Post-dose), change from Baseline to Day 7 (4 hrs Post-dose), and change from Day 7 (Pre-dose) to Day (4 hrs Post-dose) by treatment.

Paired t-test will be applied on CFB values 1) between Day 1 pre-dose and Day 7 (pre-dose) and 2) between Day 7 pre-dose and Day 7 4 hrs post-dose to determine whether the change within placebo and RP3128 is significant or not.

The CFB values in cytokine expression levels will be compared between placebo and RP3128 using an ANCOVA with the CFB values as the dependent variable, treatment as a fixed effect and corresponding baseline as a covariate. Three different types of CFB will be used: 1) CFB from Day 1 (Pre-dose) to Day 7 (Pre-dose), 2) CFB from Day 1 (Pre-dose) to Day 7 (4 hrs Post-dose), and 3) CFB from Day 7 (Pre-dose) to Day 7 (4 hrs Post-dose). The LSMeans, Standard Errors for each treatment and treatment difference will be presented together with the corresponding 95%-confidence interval and p-value.

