6 GENERAL ASPECTS FOR STATISTICAL ANALYSIS

6.1 SUMMARY STATISTICS

The standard summary statistics that will be calculated for quantitative and qualitative variables are:

- Quantitative:
 - Standard Statistics for both Safety/PK: Number of subjects, mean, median, standard deviation (SD), minimum and maximum of the raw data
 - Additional Statistics for PK: coefficient of variance (PK concentration and PK parameters), geometric mean, and geometric CV (%) (PK parameters AUC and C_{max} in SAD part and AUC₀₋₂₄, C_{max}, C_{min}, C_{trough} in MAD part)
- Qualitative: number of subjects (n), number of missing observations (nmiss), absolute and relative frequencies (%) per category.

Demographics and disposition will be summarized by treatment group and overall.

Data collected pre- and post-dose during the treatment period (e.g., vital signs, ECG, and clinical laboratory) will be summarized by treatment group (dose level), visit and/or time point. For quantitative variables (ECG measurements, vital signs, hematology, etc.), change from baseline will be calculated and summarized by treatment, visit and/or time point together with baseline and post-dose value. For qualitative variables (e.g., ECG interpretation, urinalysis), standard summary of frequencies will be calculated by treatment, visit and/or time points. For safety lab data only, shift table will be produced to present the change of reference range indicator from baseline to post-dose. PK parameters will be summarized by treatment group, and visit (if applicable). All subjects assigned and treated with Placebo in different cohorts will be pooled together and summarized as a single group.

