14 TABLE AND LISTING

The following TL shells are provided as a framework for the display of data from this study. The shells may change due to unforeseen circumstances. These shells may not be reflective of every aspect of this study but are intended to show the general layout of the Tables and Listings that will be included in the final report. Tables and Listings are numbered following the International Conference on Harmonization (ICH) structure. Table headers, variables names and footnotes will be modified as needed following a review of the blinded data and also following data analyses. Please note that all summary tables and listings will be generated using SAS® Version 9.2 or higher.

**Table 14.1.1.S/M Disposition of Subjects (SAD/MAD)
Randomized Population**

	Pooled Placebo	RP3128 25 mg	RP3128 50 mg	RP3128 100 mg	RP3128 200 mg	RP3128 400 mg	Total n (%)
Number of Subjects Randomized (N)	xx	xx	xx	xx	xx	xx	xx
Number of Subjects in Safety Population (N)	xx	xx	xx	xx	xx	xx	xx
Number of Subjects in PK Population [n (%)]	xx (xx.x%)	xx (xx.x%)	xx (xx.x%)	xx (xx.x%)	xx (xx.x%)	xx (xx.x%)	xx (xx.x%)
Number of Subjects who Completed the Study [n (%)]	xx (xx.x%)	xx (xx.x%)	xx (xx.x%)	xx (xx.x%)	xx (xx.x%)	xx (xx.x%)	xx (xx.x%)
Number of Subjects who Discontinued Early [n (%)]	xx (xx.x%)	xx (xx.x%)	xx (xx.x%)	xx (xx.x%)	xx (xx.x%)	xx (xx.x%)	xx (xx.x%)
Adverse Event	xx (xx.x%)	xx (xx.x%)	xx (xx.x%)	xx (xx.x%)	xx (xx.x%)	xx (xx.x%)	xx (xx.x%)
Allergic Reaction / Anaphylaxis	xx (xx.x%)	xx (xx.x%)	xx (xx.x%)	xx (xx.x%)	xx (xx.x%)	xx (xx.x%)	xx (xx.x%)
Concomitant Medication Interfering W/ PK	xx (xx.x%)	xx (xx.x%)	xx (xx.x%)	xx (xx.x%)	xx (xx.x%)	xx (xx.x%)	xx (xx.x%)
Emesis Within 10 hrs Post Dose	xx (xx.x%)	xx (xx.x%)	xx (xx.x%)	xx (xx.x%)	xx (xx.x%)	xx (xx.x%)	xx (xx.x%)
Lost to Follow-up	xx (xx.x%)	xx (xx.x%)	xx (xx.x%)	xx (xx.x%)	xx (xx.x%)	xx (xx.x%)	xx (xx.x%)
Physician Decision	xx (xx.x%)	xx (xx.x%)	xx (xx.x%)	xx (xx.x%)	xx (xx.x%)	xx (xx.x%)	xx (xx.x%)
Protocol Deviation	xx (xx.x%)	xx (xx.x%)	xx (xx.x%)	xx (xx.x%)	xx (xx.x%)	xx (xx.x%)	xx (xx.x%)
Serious Adverse Event	xx (xx.x%)	xx (xx.x%)	xx (xx.x%)	xx (xx.x%)	xx (xx.x%)	xx (xx.x%)	xx (xx.x%)
Study Terminated by Sponsor	xx (xx.x%)	xx (xx.x%)	xx (xx.x%)	xx (xx.x%)	xx (xx.x%)	xx (xx.x%)	xx (xx.x%)
Withdrawal by Subject	xx (xx.x%)	xx (xx.x%)	xx (xx.x%)	xx (xx.x%)	xx (xx.x%)	xx (xx.x%)	xx (xx.x%)
Other	xx (xx.x%)	xx (xx.x%)	xx (xx.x%)	xx (xx.x%)	xx (xx.x%)	xx (xx.x%)	xx (xx.x%)

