Programming Note: <Dose Level> = RP3128 25mg, 100mg, and 400mg.

X will be assigned as 1, 2, and 3 as per each RP3128 dose level.

Table 14.2.1.2.3.X.M RP3128 – Summary of PK parameters (MAD) – Day 7

**PK Population
<Dose Level>**

Cohort/Subject	C _{max} (ng/mL)	C _{min} (ng/mL)	AUC ₀₋₂₄ (ng·h/mL)	C _{av} (ng/mL)	Degree of Fluctuation	Swing	T _{max} (h)	T _{1/2} (h)
xxxx	xxx	xxx	xxx	xxx	xxx	xxx	xxx	xxx
xxxx	xxx	xxx	xxx	xxx	xxx	xxx	xxx	xxx
Statistics								
N	xx	xx	xx	xx	xx	xx	xx	xx
Mean	xxx.x	xxx.x	xxx.x	xxx.x	xxx.x	xxx.x	xxx.x	xxx.x
SD	xxx.xx	xxx.xx	xxx.xx	xxx.xx	xxx.xx	xxx.xx	xxx.xx	xxx.xx
CV (%)	xx.x	xx.x	xx.x	xx.x	xx.x	xx.x	xx.x	xx.x
Minimum	xxx	xxx	x.x	xxx	xxx	x.x	x.x	x.x
Median	xxx.x	xxx.x	xx.x	xx.x	xx.x	xx.x	xx.x	xx.x
Maximum	xxx	xxx	x.x	x.x	x.x	x.x	x.x	x.x
Geo Mean ¹	xxx.x	xxx.x	xxx.x	xxx.x	NA	NA	NA	NA
Geometric CV%	xx.x	xx.x	xx.x	xx.x	NA	NA	NA	NA

N=Number of subjects with derivable PK parameter.

¹: Geo Mean: Geometric means are based on the arithmetic means of ln-transformed values

Programming Note: <Dose Level> = RP3128 25mg, 100mg, and 400mg

X will be assigned as 1, 2, and 3 as per each RP3128 dose level.

Table 14.2.2.X.1.M Summary of Cytokines <expression value>: Change from Baseline (MAD)

Visit and Time Point	Statistic	Safety Population	
		Placebo (N=xx)	RP3128 (N=xx)
Baseline (Day 1, Pre-dose)	n	Xx	Xx
	Mean ± SD	xx.x ± x.xx	xx.x ± x.xx
	Median	xx.x	xx.x
	Min, Max	xx , xx	xx , xx
Day 7 (Pre-dose)	n	xx	Xx
	Mean ± SD	xx.x ± x.xx	xx.x ± x.xx
	Median	xx.x	xx.x
	Min, Max	xx , xx	xx , xx
Change from Baseline ¹	n	xx	Xx
	Mean ± SD	xx.x ± x.xx	xx.x ± x.xx
	Median	xx.x	xx.x
	Min, Max	xx , xx	xx , xx
	Paired t-test	x.xx	x.xx
Day 7 (4 hr Post-dose)			
Change from Baseline ¹			
Change from Baseline ²			

Note: 1 Baseline set at Day 1 pre-dose;
2 baseline set at Day 7 pre-dose

Data source: Listings 16.2.6.1

Programming note: Replace <expression value> with Th1, Th2, and Th17 and X will be assigned as 1, 2, and 3 for expression Th1, Th2 and Th17 respectively

Table 14.2.2.X.2.M ANCOVA Results of Cytokine <expression value> Change from Baseline to Day 7 (Pre-dose/Post-dose)/ Difference between Pre-dose and Post-dose on Day 7 (MAD)

Safety Population

Item	Treatment	n	LSMeans	Std Err	Difference between RP3128 to Placebo				
					LSMeans	Std Err	95%-confidence Interval	P-value Treatment	P-value Baseline
CFB Day 7 (Pre-dose)	Overall	xxx						x.xxxx	x.xxxx
	Placebo	xxx	x.xxx	x.xxx					
	RP3128	xxx	x.xxx	x.xxx	x.xxx	x.xxx	x.xxx, x.xxx	x.xxxx	

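### MAD cytokines: no planned table gives a mean or difference at 25, 100 or 400 mg, and Section 10 does not define the levels of treatment

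*SAP*

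**What the plan says.** The ex-vivo cytokine effect is a MAD secondary objective (SAP 3.2) and secondary endpoint (4.2); its analysis is in Section 10, headed exploratory.

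- **Between groups (Section 10):** "The CFB values in cytokine expression levels will be compared between placebo and RP3128 using an ANCOVA", with treatment as a fixed effect and the corresponding baseline as covariate, for three definitions of change.
- **Within groups (Section 10):** paired t-tests "to determine whether the change within placebo and RP3128 is significant or not".
- **Descriptives (Section 10):** a set of statistics ending with "change from Day 7 (Pre-dose) to Day (4 hrs Post-dose) by treatment". The levels of treatment are not given.
- **Table 14.2.2.X.1.M:** two columns, Placebo and RP3128.
- **Table 14.2.2.X.2.M:** rows Overall, Placebo and RP3128, with one contrast headed "Difference between RP3128 to Placebo".
- **Table numbering:** for cytokines, "X will be assigned as 1, 2, and 3 for expression Th1, Th2 and Th17 respectively". For the MAD PK tables, "X will be assigned as 1, 2, and 3 as per each RP3128 dose level".
- **General rule (6.1):** data collected before and after dosing "will be summarized by treatment group (dose level), visit and/or time point". The same section pools placebo across cohorts and has no matching rule for the active doses.

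There is no other cytokine table in the contents list or the shells. Listing 16.2.6.1 shows dose, but subject by subject.

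**The concern.** A three-dose escalation part should let the reader see at which dose a pharmacodynamic marker moved. As drafted, the tables give one RP3128 mean and one difference from placebo, so dose means would have to be rebuilt from the listing.

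The model is also not fixed. With treatment undefined, one programmer could fit two levels and another four, with different residual variance and degrees of freedom. The Overall row of Table 14.2.2.X.2.M carries its own treatment p-value. In a two-level model it merely repeats the RP3128-row p-value; in a four-level model it becomes a 3-df omnibus test.

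If the doses differ, the two-group model counts those differences as residual noise, which widens the interval for the average it is meant to estimate.

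**Working it through.** **Group sizes (SAP 3.5 and 3.6).** Cohorts M1, M2 and M3 each have 6 RP3128 and 2 placebo. Active 6+6+6 = 18, placebo 2+2+2 = 6, total 24, which matches the stated MAD size. Dose range 400/25 = 16-fold.

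**What the average shows.** The SAP gives no cytokine SD or effect, so the patterns below are assumptions, with the 400 mg effect set to 1.
- Only 400 mg acts: (0+0+1)/3 = 33% of the 400 mg effect.
- Rising: (1/3+2/3+1)/3 = 67%.
- Saturating: (0.75+1+1)/3 = 92%.

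**Precision in residual-SD units (ignoring baseline imbalance).**
- Average of doses minus placebo: SE = √(1/18+1/6) = 0.471.
- One dose minus pooled placebo: SE = √(1/6+1/6) = 0.577.
- One dose minus its 2 concurrent placebo subjects: SE = √(1/6+1/2) = 0.816, that is 0.816/0.577 = 1.41 times as wide.
- 95% half-widths: two-group model (21 df) 2.080 × 0.471 = 0.98; four-level average (19 df) 2.093 × 0.471 = 0.99; four-level single dose 2.093 × 0.577 = 1.21.

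**Power by simulation.** Assumed: baseline slope -0.5, residual SD 1, two-sided 5%, 8,000 runs per scenario. Entries are for 400 mg effects of 1 / 1.5 / 2 SD.

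| Pattern | Two-group ANCOVA | Average contrast, four-level ANCOVA |
|---|---|---|
| Flat | 51 / 84 / 97% | 50 / 84 / 97% |
| Saturating | 44 / 77 / 95% | 44 / 77 / 95% |
| Rising | 24 / 45 / 67% | 26 / 50 / 75% |
| 400 mg only | 8 / 10 / 11% | 11 / 17 / 26% |

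For comparison, a test of 400 mg minus pooled placebo alone has 36 / 67 / 89%. The average test beats it when effects are flat or saturating and loses to it when effects rise or only 400 mg acts.

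The bottom row follows from the residual. With only 400 mg acting at d, the sum of squares between doses is 18 × (2/9)d² = 4d². The two-group residual SD is then about √((21+4d²)/21), which is 1.33 at d = 2. The half-width becomes 2.080 × 1.33 × 0.471 = 1.30 (simulated 1.31, against 1.00 for the four-level average).

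**Limit of dose-level differences.** Cohorts are dosed in sequence (3.3) and randomised separately (3.6), so only 2 of the 6 placebo subjects are concurrent with a given dose. Suppose every M3 value shifts by c. The 400 mg mean moves by c and the pooled placebo mean by 2c/6 = c/3.
- 400 mg minus placebo: bias c - c/3 = +2c/3.
- 25 mg and 100 mg minus placebo: bias -c/3 each.
- Average of doses minus placebo: c/3 - c/3 = 0.

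Simulated with no drug effect and c = 0.5 / 1 SD (10,000 runs each):
- coverage of the 95% interval for 400 mg minus placebo falls to 92 / 83%;
- the omnibus 3-df test rejects in 9 / 26%;
- the four-level average contrast rejects in 5.0 / 4.3%, and the two-group test in 4.6 / 3.1%.

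**The case against.** **The SAP never says the active doses are pooled.** Section 6.1 equates treatment group with dose level for data collected before and after dosing, which describes the cytokine samples, and pools only placebo. On that reading dose-level descriptives are already planned and only the shell columns disagree. This stands in part. But the examples in 6.1 are vital signs, ECG and laboratory data, and Section 9.1 lets treatment group include pooled RP3128. If 6.1 governs, both cytokine shells contradict it; if not, the factor is undefined.

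**Shells are weak evidence.** Section 14 says they "are intended to show the general layout of the Tables and Listings" and allows headers to change, and one ECG shell carries doses that are not in this study. That is fair, but the ANCOVA and t-test sentences of Section 10 also name only two groups, and no text plans a dose-level cytokine comparison.

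**The average contrast is not an error.** Correct. It outperforms 400 mg minus placebo when effects are flat or saturating, and a cohort shift does not bias it. It should stay.

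**Dose-level differences are fragile.** Also correct: 6 against 6, about ±1.2 SD, and exposed to cohort shift. That is why they should be descriptive, without p-values.

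**Weight.** The section is headed exploratory, the raw values by dose are in the listing, and every power figure rests on assumed effects. These points limit the severity but leave the gap.

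**Conclusion.** The point holds, with moderate consequence: it should be corrected, but it does not threaten the trial's primary safety aims. Section 10 does not state the levels of treatment, its wording and shells point to two groups, and no planned table shows a cytokine mean or difference for any dose. That follows from the text alone.

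The size of the loss depends on the unknown dose pattern. If all doses act alike, nothing material is lost for the average effect. If only 400 mg acts, the table shows a third of its effect, and at 2 SD the two-group test has 11% power against 26% for the same contrast from a four-level model. These figures assume a baseline slope of -0.5, residual SD 1 and the stated effects, none of which the SAP supplies. Dose-level reporting would show the pattern, though imprecisely.

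**What to change.** 1. In Section 10, define treatment as four levels: pooled placebo, 25 mg, 100 mg and 400 mg.
2. In Table 14.2.2.X.1.M, give descriptive statistics and within-group changes by dose, plus RP3128 overall. Keep the paired t-test for placebo and RP3128 overall only.
3. For each of the three change definitions, fit the ANCOVA with the four-level factor and the corresponding baseline. Make the average of the three doses minus placebo the only tested comparison.
4. In Table 14.2.2.X.2.M, show each dose minus pooled placebo as an estimate with 95% CI, labelled descriptive, with no p-value and no trend test. Drop the treatment p-value from the Overall row.
5. Add a footnote: placebo is pooled over sequentially dosed cohorts, with 2 of 6 concurrent with each dose, so a cohort or assay-run shift would bias dose-level differences but largely cancels in the average.
6. For consistency with Section 10, remove visit from the ANCOVA footnote.

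**Cost.** SAP and shell wording only, with no new data and no added treatment p-values. Residual df fall from 21 to 19, and power for the average stays within 1 point of the two-group test when effects are flat. Comparing each dose with only its concurrent placebo would remove the cohort bias but widen the SE by 41%, so it is not recommended.
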